### **Setting**

This study will take place at a place consistent with the plan approved by the IRB for the ARIC study . Potential subjects will be identified by ARIC study staff in accordance with the ARIC protocol.

### **Subjects selection criteria**

- **Inclusion Criteria**

Individuals who are eligible for the ARIC study, with which this pilot study is cooperating.

- **Exclusion Criteria**

Any individuals not eligible for the ARIC study.

- **Sample Size**

The proposed study is intended to be a pilot study to examine the impact of a novel consent form methodology on participant comprehension. The proposed enrollment is 100 participants in each arm of the study for a total of 200.

**All study team members** will be trained to administer the NEAT form and the comprehension tool.

### **Outcome Measure(s)**

Following the consent process, participants will be administered the Comprehension tool to measure their comprehension. The summary scores will be used to address the primary aim of whether or not the NEAT consent form improves participant comprehension. In addition, subjects will be asked the qualitative questions about what they liked and disliked regarding the consent form. The study team member qualitative data about their opinion of using the form will also be collected at the end of the study. The comprehension score and the qualitative data about the consent form qualities as perceived by participants and study team members make up the outcomes to be measured.

### **Analytical Plan**

Study participants will be randomized 1:1 to either the traditional versus NEAT consent documents. Differences in comprehension will be assessed by the Comprehension tool, which is an instrument to assess research consent comprehension.

Summary scores from the Comprehension tool will be analyzed initially using descriptive statistics which will be helpful in planning of a larger trial in the future. To test the differences in comprehension between the two consent forms, we will use a t-test (assuming the assumptions of the test are met) and compare the summary scores. The qualitative feedback will be reviewed to see if any consistent themes are present, both overall and by group.

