## **Objectives**

This pilot study will examine the effectiveness of the New Executive and Appendix Template (NEAT) form when used in the consent process for individuals participating in the Atherosclerosis Risk in Communities (ARIC) Neurocognitive Study. Specifically, the primary objective of the study is to:

1. Determine if participants who receive the NEAT form report greater comprehension (as measured by the total score on the Comprehension tool instrument) at the end of the consent process, than participants who receive a standard form.

The secondary objectives are to:

1. Determine what types of characteristics participants value in a consent form, via a qualitative analysis of responses to the question “What do you like best, if anything about this consent form? and What do you like least, if anything about this consent form?”
2. Determine what types of characteristics study team members find helpful or burdensome when utilizing a consent form during the consent process.

Participation in the NEAT study will involve randomization of study participants to either the traditional consent form (detailing the ARIC study) or the NEAT form and the materials that accompany it (also detailing the ARIC study). The consent process will be conducted in the usual manner using the document to which the participant was randomized (NEAT or Traditional). Following the consent process, the interviewer will administer the Comprehension tool, a questionnaire which will measure participants' comprehension (Part 1) and opinions about the layout of the tool (Part 2). A qualitative analysis of the open-ended questions (Part 2) will provide subjective data on participant's opinions of the form design and arrangement, or other factors that they consider important. The Comprehension tool score and the qualitative data about the consent form qualities make up the outcomes to be measured. Ultimately, these data will provide pilot data showing whether differences in comprehension or subject preference may exist between the two consent form designs.

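### Does leaving the t-test's level, sidedness and fallback unstated undermine the primary comparison?

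*Combined protocol and SAP*

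**What the plan says.** The Objectives section names the primary outcome, the total score on the Comprehension tool, and words the aim with a direction: "Determine if participants who receive the NEAT form report greater comprehension". Outcome Measure(s) does the same, describing "the primary aim of whether or not the NEAT consent form improves participant comprehension". The Objectives section closes without a direction, saying that the pilot data will show "whether differences in comprehension or subject preference may exist between the two consent form designs".

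The Analytical Plan puts descriptive statistics first, for use in planning a larger trial, and then gives the only inferential statement: "To test the differences in comprehension between the two consent forms, we will use a t-test (assuming the assumptions of the test are met"), with the summary scores as the quantity compared. Allocation is 1:1. The sample size paragraph under Subjects selection criteria calls the study a pilot and says "The proposed enrollment is 100 participants in each arm of the study for a total of 200", with no power calculation.

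Nowhere do the documents give a significance level, a confidence level, one- or two-sided testing, pooled or Welch variance, a way to judge the assumptions, or a replacement test. Nothing on this point appears to be blacked out.

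**The concern.** Three features together look risky.

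- The clause on assumptions allows the t-test to be dropped but names nothing in its place.
- The aim has a direction while the test sentence does not, so a team could argue for a one-sided test.
- Descriptive statistics come first, so these choices could be made with group results in view.

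At stake are the false-positive rate of the primary comparison and the verdict itself: a modest observed advantage for NEAT could be significant on one reading and not on another. A one-sided reading would also be unable to report that NEAT lowers comprehension.

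**Working it through.** **Inputs.** From the documents: 100 per arm, 1:1, t-test on total scores. Assumed: a 0.05 level, because none is stated, and the score distributions used in simulation, because the tool's item count, range and SD are not in the text. Effects are therefore in SD units. The plan has no figure to reproduce, since 200 participants is given without power, effect size or SD.

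**1. Threshold for significance.** Smallest significant observed difference = critical t(198) × √(2/100), where √(2/100) = 0.1414.

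- Two-sided 0.05: 1.972 × 0.1414 = 0.279 SD.
- One-sided 0.05: 1.653 × 0.1414 = 0.234 SD.
- One-sided 0.025: same critical value as two-sided 0.05, so 0.279 SD.

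**2. Chance of declaring NEAT better** (noncentral t, 198 degrees of freedom).

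| True difference | One-sided 0.05 | Two-sided 0.05, or one-sided 0.025 | Gap (points) |
|---|---|---|---|
| 0.20 SD | 40.7% | 29.0% | 11.7 |
| 0.25 SD | 54.7% | 42.0% | 12.7 |
| 0.30 SD | 68.1% | 56.0% | 12.1 |

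The gap comes from letting the false NEAT-is-better rate be 5% instead of 2.5%. Run the one-sided test at 0.025 and it vanishes.

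**3. Does the natural reading hold its level?** Three null simulations were run with 20,000 replicates each (simulation standard error √(0.05 × 0.95/20,000) = 0.15 points): normal scores and two 10-item patterns bunched near the top of the scale. The two-sided t-test rejected in 5.2%, 5.2% and 4.9%. Welch gave the same figures, as expected: with equal arms the pooled and Welch standard errors are identical and only the degrees of freedom differ. A wider grid of 50 beta-binomial settings (10 to 100 items, mean 50% to 90% correct, intraclass correlation 0.1 or 0.2, 10,000 trials each) gave 4.3% to 5.4% for Welch.

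**4. Does acting on the assumptions clause inflate error?** A fixed rule was tried in the same three patterns: Shapiro-Wilk test, then t-test or Mann-Whitney (4,000 replicates, standard error 0.34 points). It rejected in 5.3%, 5.3% and 4.9%. In the two bunched patterns Shapiro-Wilk rejected normality every time, so the rule amounted to always using Mann-Whitney. Switching on the shape of the scores kept the level.

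**5. What if the choice follows the result?**

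| Behaviour | Three patterns | 50-setting grid |
|---|---|---|
| Keep the better of t-test (Welch in the grid) and rank-sum, two-sided | 6.1% to 6.2% | 5.1% to 7.8% |
| t-test, one- or two-sided, whichever is significant | 7.4% to 7.8% (theory 5% + 2.5% = 7.5%) | 6.8% to 8.0% |
| Test and sidedness both open | 9.0% to 9.2% | 7.6% to 11.3% |

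In a rerun of 30 settings, the last row was about 7.6% to 9.7% at mean scores of 50% to 70%; it reached or passed about 10% only at an assumed mean of 90% correct.

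**6. Would naming one test now gain power?** Not predictably. Welch was 1 to 18 points ahead of rank-sum when wrong answers were corrected at random. Rank-sum was 5 to 17 points ahead for a uniform shift from 90% to 94% correct. The answer follows the assumed score pattern, which the documents do not give.

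**The case for a change.** The strongest case for a change is that prespecification cannot be restored once scores are seen, and that writing down the test, sidedness and level costs a sentence or two and no participants. The directional objective makes a one-sided test arguable, and an observed advantage between 0.234 and 0.279 SD would then get opposite verdicts from the same data.

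The omission stands: the level and sidedness are not in the documents, and a reader cannot confirm the chosen analysis from the text alone. The step from omission to harm is weaker. The only sentence describing the test speaks of a difference, no section mentions one-sided testing, and pairing a directional aim with a two-sided test is normal practice. The split verdict also needs the one-sided test to be run at 0.05. The inflated error rates describe a team that runs several tests and keeps the best p-value, which the plan nowhere invites. Looking at descriptive statistics first is ordinary practice; in the check above, a switch driven by the shape of the scores left the level intact.

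**Conclusion.** The plan is incompletely specified on this point, not wrong. An analyst following it would run a two-sided t-test of NEAT against traditional scores, and at 100 per arm that test keeps its level (4.3% to 5.4%) across the score patterns tried, including strongly bunched ones. Pooled or Welch makes no practical difference with equal planned arms. Harm requires choosing by result: about 5% to 8% error for choice of test, about 8% to 11% with sidedness open too. These figures assume a 0.05 level and the simulated score distributions.

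No stated rule gives a wrong or worse answer, and fixing one test in place of another has no predictable gain in power. For a pilot meant to inform a larger trial, a result between 0.234 and 0.279 SD changes a significance label but leaves the mean difference and SD as they are. This is a gap that analysts fill sensibly by default, so no change to the plan follows.

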### **Confidentiality and Privacy**

Confidentiality will be protected by collecting only information needed to assess study outcomes, minimizing to the fullest extent possible the collection of any information that could directly identify subjects, and maintaining all study information in a secure manner. To help ensure subject privacy and confidentiality, no identifying information will be collected with the Comprehension tool form or likes/dislikes feedback. Subject identifiers will not be linked to any personally identifiable information. The comprehension tool will be conducted on paper directly after the consent process. After the tools are collected, they will be scored by the PI and then entered into REDCap for analysis. Data access to the data collection forms and the transcribed information in the electronic system will be limited to study team members. Data and records will be kept on the WF School of Medicine

campus in a locked office, and computer data will be password protected and secured on the WFBH network. No reference to any individual participant will appear in reports, presentations, or publications that may arise from the study.

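### Does the theme review of participants' opinions by consent form need a coding rule, per-arm counts and a masked reader before it can be relied on?

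*Combined protocol and SAP*

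**What the plan says.** The first secondary objective (Objectives) is to "Determine what types of characteristics participants value in a consent form, via a qualitative analysis of responses to the question" of what participants liked best and least about the form. Outcome Measure(s) repeats that "subjects will be asked the qualitative questions about what they liked and disliked regarding the consent form" and counts the answers among the outcomes, without giving a method. The method is a single sentence in the Analytical Plan: "The qualitative feedback will be reviewed to see if any consistent themes are present, both overall and by group".

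The Objectives section ends with a statement that goes beyond the numbered objectives: "Ultimately, these data will provide pilot data showing whether differences in comprehension or subject preference may exist between the two consent form designs".

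On handling of the completed forms, Confidentiality and Privacy says: "After the tools are collected, they will be scored by the PI and then entered into REDCap for analysis". It does not mention masking. On numbers, Subjects selection criteria says: "The proposed enrollment is 100 participants in each arm of the study for a total of 200". The only hypothesis test in the plan is a t-test on the comprehension summary score.

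The Comprehension tool, with its qualitative section, is listed as an appendix, but its content is not in the text available for this review.

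**The concern.** The closing statement of the Objectives names comprehension and preference together, yet the plan treats them very differently. Comprehension gets descriptive statistics and a t-test. Preference gets a reading for themes, overall and within each arm, with no definition of a consistent theme, no coding frame, no count per arm and no statement that the reader is unaware of which form was used.

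Each participant sees one form only, so the answers are opinions of the form received, not a choice between two forms. A reader who knows the arm and hopes the new form does well might find more praise in one pile than in the other. Even an impartial reader comparing two sets of 100 answers by eye could take a chance imbalance for a real one. The pilot report might then say that participants preferred one design when the data do not support it.

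**Working it through.** **Inputs from the documents.** 100 participants per arm, 200 in total (Subjects selection criteria); 1:1 allocation (Analytical Plan). The arithmetic agrees: 2 × 100 = 200. The plan gives no other figure on this point, so there is nothing further to reproduce.

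**Assumptions, not in the documents.** All 100 in each arm answer; a theme is raised with the same true probability p in both arms, with p from 10% to 50%; 5 or 10 themes are compared; themes are independent; a gap of g or more people would be noticed, with g = 10 or 15.

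**Step 1: one theme.** Let X₁ and X₂ be independent Binomial(100, p) counts. The exact chance of a gap is P = Pr(|X₁ − X₂| ≥ g).

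**Step 2: several themes.** The chance of at least one such gap among K independent themes is 1 − (1 − P)^K. For p = 10%, g = 10 and K = 10, P = 0.0251 and 1 − (0.9749)^10 = 0.22.

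| p | one theme, gap ≥ 10 | 5 themes, gap ≥ 10 | 10 themes, gap ≥ 10 | one theme, gap ≥ 15 | 10 themes, gap ≥ 15 |
|---|---|---|---|---|---|
| 10% | 2.5% | 12% | 22% | 0.07% | 0.7% |
| 20% | 9.3% | 39% | 62% | 1.0% | 10% |
| 30% | 14.2% | 54% | 78% | 2.5% | 22% |
| 50% | 17.9% | 63% | 86% | 4.0% | 34% |

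For a rarer theme, p = 5%, a gap of 10 or more has a chance of 0.2% for one theme and 2.4% across ten.

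The result therefore depends heavily on the cut-off. For ten themes at 10% to 50% prevalence, moving it from 10 to 15 people takes the range from 22%–86% to 0.7%–34%. The plan has no cut-off, and a review that does not count participants would produce no such gap to judge.

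**Step 3: would counts and intervals cure it?** With counts, the 95% half-width for a difference between arms is 1.96 × √(2p(1 − p)/100):

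- p = 10%: 1.96 × 0.0424 = 0.083, about 8 points
- p = 20%: 1.96 × 0.0566 = 0.111, about 11 points
- p = 30%: 1.96 × 0.0648 = 0.127, about 13 points
- p = 50%: 1.96 × 0.0707 = 0.139, about 14 points

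These show the uncertainty of each theme but do not control error across themes. At a nominal 5% each, the chance of at least one false difference is 1 − 0.95⁵ = 23% for five themes and 1 − 0.95¹⁰ = 40% for ten. Only presenting the differences as exploratory deals with that.

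**Step 4: what does the plan claim from these data?** The numbered objective asks what participants value, which is descriptive. The by-group wording can be met by listing the themes found within each arm. The closing statement of the Objectives says only that differences may exist, and calls the data pilot data. The use of results in planning a larger trial is attached in the Analytical Plan to the comprehension scores, not to the opinions. Nowhere does a test, ranking or decision rest on the theme review.

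**The case for a change.** The strongest case for a change is that the comparison between forms is the protocol's own: it plans a review by group and speaks of differences in preference. The remedy also looks cheap. It would need a short coding frame, a second reader for up to 400 short answers (200 participants × 2 questions), and counts by arm, with no burden on participants and no effect on the primary comparison. For common themes the arithmetic is real: a chance gap of 10 people somewhere among ten themes is more likely than not once prevalence reaches 20%.

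Part of this stands. The coding method is not written down, and preference is a loose word for opinions gathered from people who each saw one form. A report giving the number of participants raising each theme in each arm, and calling any contrast exploratory, would be clearer than one that did not.

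The rest does not carry a change to the plan:

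- Counts and intervals for free-text themes are one accepted way to report qualitative data, not the only one.
- Two masked readers cost extra work, and masking would be partial because an answer that mentions the folder or the overview reveals the form.
- Rewording preference alters no result.
- The text does not show that an unmasked reader's impression will be the only evidence. The statement that the principal investigator scores the tools most naturally refers to the comprehension score; nobody is named as reader of the open answers; and the unseen appendix may contain a rating item.

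**Conclusion.** No change to the plan is needed. This is missing detail about a qualitative, secondary outcome in a pilot, of a kind that analysts settle sensibly when they code and report the answers. Following the plan as written produces no wrong result: no inference on opinions is specified, the listed objectives can be met, and the t-test on comprehension is unaffected.

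The possible harm is an over-read imbalance in the report. Its chance, for ten themes at 10% to 50% prevalence, runs from 0.7% to 86% depending on whether a gap of 15 or of 10 people is taken as notable. That range rests on assumed prevalence, number of themes, independence, full response and cut-off, none of which the documents supply. Themes drawn from the same short answers are likely to overlap, which makes independence doubtful.

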### **Human Subjects Protection**

### **Subject Recruitment Methods**

Describe how and where subjects will be identified and recruited. Indicate who will do the recruiting, and tell how subjects will be contacted. Describe efforts to ensure equal access to participation among women and minorities. Describe how you will protect the privacy of potential subjects during recruitment.

- Under this limited waiver, you are allowed to access and use only the minimum amount of PHI necessary to review eligibility criteria and contact potential subjects. What information are you planning to collect for this purpose?
  - Participants in this study are members of the ongoing ARIC study.
- How will confidentiality/privacy be protected prior to ascertaining desire to participate?
  - Participants in this study are members of the ongoing ARIC study.
- When and how will you destroy the contact information if an individual declines participation?
  - The IRB approved processes for the destruction of contact information will be utilized as usual with no necessary changes required by the NEAT study. The NEAT study will not involve the recording of any subject identifiers at any time.

### **Informed Consent**

A waiver of the requirements for **signed** informed consent is requested for the study team members who will provide anonymized feedback on the pros/cons of using the two consent forms. The justification for a waiver of signed consent is presented below.

The research presents no more than minimal risk of harm to subjects and involves **no** procedures for which written consent is normally required outside of the research context. Study team members are simply providing information on the effectiveness of a form to communicate information (ARIC participants) and the usability of the form.

### **Confidentiality and Privacy**

Confidentiality will be protected by collecting only information needed to assess study outcomes, minimizing to the fullest extent possible the collection of any information that could directly identify subjects, and maintaining all study information in a secure manner. To help ensure subject privacy and confidentiality, no identifying information will be collected with the Comprehension tool form or likes/dislikes feedback. Subject identifiers will not be linked to any personally identifiable information. The comprehension tool will be conducted on paper directly after the consent process. After the tools are collected, they will be scored by the PI and then entered into REDCap for analysis. Data access to the data collection forms and the transcribed information in the electronic system will be limited to study team members. Data and records will be kept on the WF School of Medicine

campus in a locked office, and computer data will be password protected and secured on the WFBH network. No reference to any individual participant will appear in reports, presentations, or publications that may arise from the study.

### **Data and Safety Monitoring**

The principal investigator will be responsible for the overall monitoring of the data and safety of study participants. The principal investigator will be assisted by other members of the study staff.

### **Reporting of Unanticipated Problems, Adverse Events or Deviations**

Any unanticipated problems, serious and unexpected adverse events, deviations or protocol changes will be promptly reported by the principal investigator or designated member of the research team to the IRB and sponsor or appropriate government agency if appropriate.

### **Appendix**

- A. Comprehension tool Form and Qualitative Assessment of Participant Perception
